## I. Abstract:

**Background:** Several clinical trials are underway to investigate if variable forms of vitamin D (D2 vs. D3) prescribed at different doses (10,000-50,000 IUs/week) can improve the side-effects associated with treatment for estrogen receptor positive (ER+) breast cancer, specifically aromatase inhibitors (AIs.) Presumably for generalizability and potential safety purposes, these trials predominantly exclude women with metastatic breast cancer (MBC); a rapidly expanding sector of the cancer survivor population who experience significant treatment-related side-effects. Evaluation of the safety of vitamin D3 supplementation is crucial since supplementation can lead to hypercalcemia and importantly, *in vitro* studies have shown that vitamin D3 influences the transcription of a gene that increases estrogen production. To assure that vitamin D3 does not abrogate the clinical effects of anti-estrogen therapies, the effect of vitamin D3 supplements on estrogen production requires an evaluation that further explores and defines its potential role in symptom management for this population.

**Objectives:** This pilot study will evaluate the feasibility of vitamin D3 supplementation (n=25) in women with MBC, providing much needed data on the preliminary safety and efficacy of this treatment in this patient population. This study will determine: 1) if weekly supplementation of high dose vitamin D3 increases serum levels of 25(OH)D without adverse effects *related* to such therapy (primary aim); 2) the effects of vitamin D3 supplementation on symptom management (secondary aim); and 3) if vitamin D3 supplementation is associated with improved biomarkers of inflammation (exploratory aim.) Additionally, we will examine the prevalence of symptoms and quality of life in (n=25) women with advanced breast cancer who have normal serum levels to investigate associations with biomarkers of inflammation.

**Methods:** . Adult, female patients (≥18 years) with ER+ MBC (Stage IV) of any race/ethnicity will be recruited from within and around LUMC. Women with a serum 25(OH)D <30 mg/dl will be invited to participate in an 8 week “proof of concept” study. Following current clinical practice guidelines, eligible participants will receive 50,000 IUs of vitamin D3 weekly for 8 weeks. Laboratory values (e.g., serum 25(OH)D, calcium, , serum estradiol), muscle function and inflammatory biomarkers (e.g.,CRP) will be examined pre- and post-supplementation, while symptoms (pain, sleep, fatigue, mood, and overall quality of life) will be assessed at baseline, 4 and 8 weeks post-supplementation. We will assess if increases in serum 25(OH)D are associated with clinically significant changes in serum estradiol, improvements in symptoms and QOL, and decreased inflammation, controlling for sunlight exposure, diet, physical activity and body composition. Women with a serum 25(OH)D ≥ 30 mg/dl who do not require supplementation will be invited to complete the study questionnaires at baseline.

**Significance/Impact:** Vitamin D3 may be a cost-effective, adjuvant therapy to combat the side-effects of treatment, to increase medication adherence and to enhance supportive care in this unique population in need of evidence-based strategies. These findings will help to characterize symptom burden in this growing population and to demonstrate the feasibility of this clinical trial. Ultimately, these data will provide novel, preliminary data to justify a larger randomized trial.

## II. Background

Breast cancer accounts for more than one-fourth of all new cancer diagnoses among women in the United States, with more than 232,000 new cases estimated for the year 2013. Despite the advances in the management of this disease, a significant number of women will go on to develop metastatic breast cancer (MBC), typically reflecting spread to the bone, lungs or viscera. Johnson et al recently showed that the incidence of MBC *at diagnosis* is increasing, showing greater disparities among younger women (aged 25-39) and minority populations. However, the introduction of novel targeted therapies, in particular treatments for HER-2 positive disease, has altered the natural history of advanced breast cancer, with an unprecedented impact on survival from such treatments. As such, the number of women living with MBC will continue to grow, reflecting a unique, rapidly expanding sector of the cancer survivor population with considerable supportive care needs that are largely unknown.

a. MBC and QOL: Cancer-related QOL is a complex entity, taking into account physical, psychological, social and sexual factors. It is an important outcome measure in all patients with breast cancer, but it is critical in the metastatic population since the disease is no longer considered curative and treatments are dictated by QOL. Although QOL has been examined extensively in women with early stage breast cancer, fewer studies have focused on women with MBC. Using a cross-sectional study design, Reed et al examined the QOL and supportive needs of women (n=235) with MBC. QOL was significantly lower in women with MBC compared to women with earlier stage disease ( $89.0 \pm 21.8$  vs.  $112.8 \pm 20.9$ , respectively). Thirty-four percent reported high levels of pain and 38% complained of significant fatigue, suggesting that symptom control was inadequate. In a smaller study, Meisel et al reported good QOL among long-term (>5 years) survivors of MBC (n=18), yet these women reported significant anxiety and depression. Additional work is needed to more comprehensively identify symptoms and to implement and test appropriately tailored therapies.

b. MBC and vitamin D: Low levels of serum 25(OH)D at the time of diagnosis have been shown to predict recurrence and death, underscoring the clinical significance of widespread vitamin D deficiency/insufficiency reported among breast cancer survivors. Purportedly 1,25 (OH)2D has been shown to induce cell-cycle arrest, increase expression of receptor activator of nuclear factor κB ligand, and down regulate the expression of cyclooxygenase-2. Hence, sufficient levels of vitamin D are needed to favorably impact breast cancer biology. In women previously diagnosed and treated for breast cancer, the prevalence of vitamin D deficiency/insufficiency is ~75%, yet these studies predominantly focused on women with early disease (Stage I-III). Vitamin D studies conducted in women with MBC are limited, but report similar prevalence estimates with lower overall levels of serum vitamin D.

[figure not shown]
c. Breast cancer treatment and symptom management: For women with estrogen receptor positive (ER+) disease, aromatase inhibitors are considered a frontline therapy, since they efficiently and effectively decrease circulating estrogen by halting the conversion of androgens to estrogen. Unfortunately, arthralgias and myalgias are highly prevalent within weeks of initiation and may result in discontinuation. The etiology of these musculoskeletal disturbances is not well understood; however, it has been postulated that estrogen itself has analgesic properties and that cytokines, such as IL-1, TNF-α, are suppressed with higher levels of estrogen. It has been further suggested that cartilage turnover increases as estrogen decreases, and that the combination of efficient estrogen deprivation combined with low serum 25(OH)D accentuates muscle and joint pain. Thus, low levels of estrogen are associated with reduced pain tolerance and increased inflammation. Additionally, breast cancer treatment is accompanied by a myriad of endocrine symptoms, including weight gain, fatigue and mood swings. In non-breast cancer populations, vitamin D supplementation has been shown to regulate weight, mood and to decrease inflammation.

d. **Significance**: A diagnosis of MBC is accompanied by a multitude of physiologic and psychological sequelae. Managing symptoms to maintain an optimum quality of life (QOL) is the major goal of care in the metastatic setting because all therapy is considered palliative. For women with ER+ breast cancer

(~75% of cases), therapies primarily target decreasing the production and absorption of estrogen. These reductions in circulating estrogen are associated with significant bone loss, arthralgia and myalgia, limiting adherence and compromising QOL. The pathophysiology of these side-effects may involve sub-optimal vitamin D status, which may be more pronounced in a hypoestrogenic environment. Therefore, supplementation with vitamin D3 (cholecalciferol) shows promise as a cost-effective, adjuvant therapy to combat the side-effects of treatment, to increase medication adherence and to enhance supportive care. However, preliminary data are critical to demonstrating the safety of high dose vitamin D3 supplementation in this unique patient population and to evaluate if this therapy has a favorable impact on symptom management and possibly inflammation. Ultimately, this study could provide insights into improving QOL and offer novel, preliminary data to justify a larger randomized trial.

### e. Conceptualization

For this study, we hypothesize that low levels of vitamin D are highly prevalent among women with MBC and that repletion to achieve serum 25(OH)D levels  $\geq 30$  mg/dl will be safe. We are also postulating that

the therapeutic effects of serum vitamin D normalization will be associated with improvements in symptom management and biomarkers of inflammation. (Depicted in Figure 1) The association between vitamin D deficiency and inflammation has been recognized from observational studies and administration of vitamin D has been shown to improve inflammatory markers in non-cancer patient populations. Mechanistically, 1,25-dihydroxyvitamin D3 (the active form of vitamin D) inhibits the production of pro-inflammatory cytokines (ex, IL-6, IL-1 $\beta$ , TNF $\alpha$ ) leading to reduced T cell activation and reduced secretion of these cytokines.

### f. Preliminary work:

Prior work in women with MBC: To explore the diet and physical activity habits of women with MBC, we recruited 25 women with advanced disease from two university hospitals over a 4 month period. Eligible women were identified by their medical oncologist (Drs. [name] and [name]) and referred to [name] (PI). Demographic and medical information was collected, and questionnaires were completed to quantify nutritional symptoms, physical activity, quality of life, functional performance and dietary intake. Participants were 58.8 ( $\pm 12.7$ ) years of age, predominantly minority (n=15) and had been living with MBC for 37 ( $\pm 29$ ) months. Dietary supplements were used by 68% (n=17) of women. The majority had an Eastern Cooperative Oncology Group (ECOG) performance status 0-1 (n=20) and most (n=13) had only received one or two different drug therapies to treat their disease, signifying a relatively healthy subset of MBC patients.

Overall QOL was lower when compared to other women with breast cancer (107  $\pm$  20 vs. 119  $\pm$  18) but higher compared to other women with MBC (107  $\pm$  20 vs. 89  $\pm$  22), respectively. These participants displayed lower physical well-being compared to other breast cancer survivors (22  $\pm$  5 vs. 24  $\pm$  5, p=0.05), with 92% (n=23) of women reporting pain symptoms and 60% (n=15) reporting fatigue. We acknowledge that patients with greater disease acuity were not approached for study inclusion, reflecting an inherent selection bias. As such, we believe our findings overestimate QOL and underestimate symptom reports in the broader MBC population. Despite these limitations, we believe these findings highlight that interventions targeting the supportive care needs of these women are greatly needed and desired.

### III. Study Aims

Several clinical trials are underway to investigate if vitamin D2 or D3 provided at various doses (10,000-50,000 IUs/week) can improve the side-effects associated with anti-estrogen therapies, specifically aromatase inhibitors (AIs). However, these current trials use variable forms of vitamin D and predominantly include women with Stage I-III disease, excluding women with metastatic breast cancer. Evaluation of the safety of vitamin D3 supplementation is crucial since supplementation can lead to hypercalcemia and importantly, *in vitro* studies have shown that vitamin D3 influences the transcription of a gene that increases estrogen production. To assure that vitamin D3 does not abrogate the clinical effects of anti-estrogen therapies, the effect of vitamin D3 supplementation on estrogen production requires evaluation. Therefore, the overarching goal of this pilot study is to evaluate the safety, feasibility and efficacy of vitamin D3 supplementation in women with MBC. We will address and test the following aims and hypotheses, respectively:

**Aim 1:** To determine if weekly supplementation of 50,000 IUs of vitamin D3 raises serum levels of 25(OH)D to >30 mg/dl without adverse effects.

**Hypothesis 1:** Women who are compliant with vitamin D3 supplementation, as evidenced by normalization (>30 mg/dl) or increases in their serum 25(OH)D levels, will not experience significant changes in serum calcium or serum estradiol levels.

**Aim 2:** To determine the effect of vitamin D3 supplementation on symptom management.

**Hypothesis 2:** Women who achieve serum concentrations of 25 (OH)D ≥30 mg/dl or experience significant increases in 25(OH)D will exhibit improvements in pain, fatigue, sleep, mood, muscle function and overall quality of life.

**Exploratory Aim:** To explore the mechanistic effects of serum vitamin D levels and vitamin D3 supplementation on inflammatory markers and potential associations with symptom management.

**Summary:** Evidence from studies involving early stage breast cancer participants confirms that musculoskeletal pain, endocrine related symptoms and mood disturbances are commonly associated with breast cancer treatment, particularly hormone deprivation therapies. The high prevalence of vitamin D deficiency/insufficiency among breast cancer survivors is well accepted and further hypothesized to aggravate treatment-related side effects, particularly arthralgias. Women with MBC are excluded from the majority of on-going vitamin D supplementation trials for safety and generalizability purposes. However, novel therapies are continuing to improve and prolong the lives of these women, resulting in a rapidly expansive group of breast cancer survivors. While vitamin D supplementation is prescribed to correct an underlying nutrient deficiency in the clinical context of preserving bone health, emerging evidence suggests it may have more systemic effects. Thus, vitamin D repletion/supplementation has profound potential implications for women with MBC, whose primary goal of treatment is to minimize the side-effects of treatment in support of optimal quality of life. This study reflects a highly innovative, yet simple therapy that could ultimately provide these survivors with a much needed evidence-based supportive care strategies.

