## **V. Study Design**

**a. Research design:** This study is comprised of an intervention arm (Group 1) and non-intervention arm (Group 2). For eligible women with low serum levels of vitamin D, we propose an 8 week open label, single arm “proof of concept” study to address concerns regarding vitamin D3 dosing, to monitor important laboratory parameters and to assess potential effects on short-term outcomes. While a randomized controlled trial (RCT) has been the traditional model to evaluate the efficacy of vitamin D supplementation, this design may be considered premature until the safety of this therapy has been evaluated in a patient population with the potential for high clinical acuity. For the women who meet all eligibility criteria except they have normal serum levels of vitamin D (Group 2), we will assess their symptomology and test associations with the biomarkers of inflammation.

**b. Study population:** Adult females with ER+ MBC can participate in the present study provided they are under the care of medical oncologist and meet all eligibility criteria. Women with early stage disease (Stages 0-3) or women with MBC who are ER- are unable to participate in this study.

**c. Sample size and power considerations:** Because this is a pilot project that will assess the feasibility, preliminary safety and short-term efficacy of a vitamin D3 intervention in this population, typical sample size calculations will not be employed. We will assess symptoms at baseline for all participants to establish prevalence estimates and at three time points in the intervention group to help increase our abilities to detect changes over time. Because of the high prevalence of vitamin D deficiency among breast cancer survivors (~75%) and the high volume of patients seen at LUMC and by [name] (collaborator), we anticipate that we can successfully recruit and enroll 50 women who meet the eligibility criteria. Our goal is to recruit 25 women for the intervention arm. Factoring in an attrition rate of ~20%, we should have complete data on 20 women who complete the intervention. This sample size is sufficient to demonstrate feasibility and will allow for the generation of effect size and variance estimates, as well as confidence interval widths around these estimates for future applications.

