### **VIII. Data Management and Analyses**

All hard copies of the data will be kept in a folder, in a locked file cabinet in a locked office in a secure building. Data will be double-entered into appropriate data management software, correcting all data entry errors prior to import into SAS (v 9.2) for statistical analyses.

Standardized descriptive statistics including means, median, standard deviations, frequency and ranges for continuous variables will be calculated to describe the participants and the overall and subscale means for the respective instruments. For specific aim 1, the number of participants who achieve sufficient levels of serum 25(OH)D will be calculated, and paired t tests will be used to assess differences between mean laboratory values from baseline and follow up. Using logistic regression, we will also explore the clinical characteristics of those who achieve sufficient levels vs. those who remain insufficient after the intervention. For specific aim 2, repeated measures analyses will be conducted to examine changes in symptom scales from baseline to interim and follow up.

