Protocol title: Safety, feasibility and efficacy of vitamin D supplementation in women with metastatic breast cancer (SAFE-D)

NCT: 02186015

Date: November 14, 2018

Protocol title: Safety, feasibility and efficacy of vitamin D supplementation in women with metastatic breast cancer (SAFE-D)

Principal Investigator: [name], RD

Research Team: [name], MS; [name], [name], RN; [name]; [name];

Statistical Analyses Conducted

Descriptive statistics were conducted to examine differences in sociodemographics, medical characteristics and dietary intake stratified by sufficient vs. insufficient serum 25(OH)D at baseline. Statistical differences between groups were assessed with Wilcoxon rank sum tests for continuous variables and chi-square or Fisher's exact test for nominal variables. Among those treated with 8 weeks of high dose cholecalciferol, changes from baseline were assessed with Wilcoxon signed rank tests for continuous scores. Analyses were performed with SAS version 9.4 (Cary, NC). A p value of <0.05 was used to denote statistical significance and based on the exploratory nature of this study, a p value of <0.10 was used to designate statistical trends.

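### Hypothesis 1 predicts no significant change in calcium or estradiol, but the plan names only difference tests in about 20 women, which cannot support that prediction; the gap is mainly in the estradiol conclusion

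*Protocol*

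**What the plan says.** The aims section introduces its hypotheses with "We will address and test the following aims and hypotheses, respectively". Hypothesis 1 concerns women judged compliant because their 25(OH)D normalised or increased, and says that they "will not experience significant changes in serum calcium or serum estradiol levels".

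For Aim 1, Section VIII of the protocol says that "the number of participants who achieve sufficient levels of serum 25(OH)D will be calculated" and that "paired t tests will be used to assess differences between mean laboratory values from baseline and follow up". The count applies to 25(OH)D only.

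The SAP says that among treated women "changes from baseline were assessed with Wilcoxon signed rank tests for continuous scores". It sets significance at p<0.05 and adds that "a p value of <0.10 was used to designate statistical trends". It does not say whether laboratory values belong to these scores.

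Three other places bear on the point:
- The abstract says the investigators will assess whether "increases in serum 25(OH)D are associated with clinically significant changes in serum estradiol". Neither Section VIII nor the SAP takes this analysis up.
- Section V.c declines a formal sample size calculation, expects 20 completers from 25 recruited, and promises effect size and variance estimates with "confidence interval widths around these estimates for future applications". It names no endpoint.
- Section VII.c lists a clinically significant estradiol increase as a reason to take a woman off study, without a number. For calcium, Section VII gives 10.5 and 11.5 mg/dL.

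**The concern.** A test for a difference can contradict a no-change hypothesis. When it fails to reject, it leaves the question open, and in a small sample it often fails to reject when a real change exists. The plan says Hypothesis 1 will be tested, yet names no analysis whose favourable outcome would support it.

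Estradiol is where this matters most. Section III gives a possible effect on estrogen production as a main reason why safety must be evaluated in women on anti-estrogen therapy, and Section IX.a says the findings will help design and justify a larger trial. If the report says only that estradiol did not change significantly, that sentence could be carried forward as reassurance that 20 women cannot give. Calcium is less exposed, because numeric individual limits exist, although no analysis text counts the women above them.

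**Working it through.** **Inputs.** 25 women recruited to the intervention arm and about 20% attrition (Section V.c); significance at 0.05 and trend at 0.10 (SAP). Sidedness is not stated, so two-sided is assumed. The documents give no SD for the change in either analyte, so effects are in units of that SD.

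**Plan's own figure.** 25 × (1 − 0.20) = 20 completers. This reproduces. No power, effect size or margin is stated, so there is nothing further to reproduce.

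**Reading 1: significance is statistical.**

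*Interval width.* Half-width = t(0.975, n−1)/√n.
- n=20: 2.093/4.472 = 0.468 SD.
- n=25 (no dropout): 0.413 SD.

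With n=20, p≥0.05 means the observed mean change lies within 0.468 observed SD of zero. The far end of the interval then lies between 0.47 SD (observed change zero) and at most 0.94 SD (p exactly 0.05).

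*Power of the paired t test.* Noncentral t with n−1 degrees of freedom and noncentrality d√n. For d=0.5 and n=20 the noncentrality is 0.5 × 4.472 = 2.236.

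| True mean shift (SD) | Power, n=20 | Power, n=25 |
|---|---|---|
| 0.2 | 13.6% | 16.1% |
| 0.3 | 24.7% | 30.2% |
| 0.5 | 56.5% | 67.0% |

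At 0.5 SD and n=20 the test misses the shift 100 − 56.5 = 43.5% of the time. Power of 80% needs a shift of 0.66 SD (0.58 SD at n=25). The signed-rank test, simulated with normal changes, has 54.3% power at 0.5 SD and n=20, so it misses about 46%. That figure matters only if the SAP test covers laboratory values.

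Hypothesis 1 is limited to women whose 25(OH)D rose. Neither analysis text makes that restriction; if it were applied, n could fall below 20 and the interval would widen.

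**Reading 2: significance is clinical.** The abstract, Section V.d and Section VII.c all use the clinical term for estradiol. Hypothesis 1 would then call for a count of women with such a change. Section VIII counts only 25(OH)D sufficiency, and the SAP specifies no count of women with such a change. For estradiol the criterion has no number.

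Even a clean count would say a limited amount. With zero events, the upper end of the exact two-sided 95% interval is 1 − 0.025^(1/n), and the one-sided 95% bound is 1 − 0.05^(1/n).

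| Events | Two-sided 95% upper limit | One-sided 95% bound |
|---|---|---|
| 0/20 | 16.8% | 13.9% |
| 0/25 | 13.7% | 11.3% |

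**The association in the abstract.** Relating the rise in 25(OH)D to estradiol change would not fill the gap: absence of an association is not absence of change.

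**The case against.** The strongest reply is that the study is an openly declared pilot of feasibility, preliminary safety and short-term efficacy, and that the SAP calls it exploratory. Low power is therefore no fault in itself. This stands; the point asks for no more patients, only for a conclusion that fits the data.

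Second, the clinical reading of significance is well supported by the abstract and Sections V.d and VII.c, and on that reading the p value does not decide Hypothesis 1. This also stands, and it narrows the defect to a reporting gap: no count is planned, and the estradiol criterion has no number.

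Third, Section V.c already promises interval widths. It names no endpoint and so excludes none. A reader might infer that intervals for the laboratory values were never intended, but the text does not show that. It shows only that neither Section VIII nor the SAP carries them forward for calcium or estradiol.

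Fourth, a reader might infer that women with a marked rise would go unnoticed. The documents do not support this. Section VII makes every treated woman evaluable for toxicity under CTCAE, sets calcium limits and an estradiol off-study criterion, and requires safety reviews after 7, 19 and 25 patients. Those provisions protect participants and inform whether the study continues. They do not say how Hypothesis 1 is to be concluded.

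**Conclusion.** The point holds as a gap between Hypothesis 1 and the analyses named for it, mainly in the estradiol conclusion. On the statistical reading, a non-significant result in about 20 women cannot support the hypothesis: the half-width is 0.47 SD and a true 0.5 SD shift is missed about 44% of the time. On the clinical reading, the needed counts are absent from both analysis texts and the estradiol criterion has no number.

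The power figures assume two-sided 0.05, 20 completers and roughly normal changes. No document gives an SD, so none of them can be translated into assay units or tied to a clinically important rise.

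A reader might go further and infer that the plan treats p≥0.05 as proof of safety. No sentence says so; the harm arises only if the conclusion is drawn from the p value. With that condition, and with individual monitoring in place, this should be fixed, but it is of minor to moderate weight.

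**What to change.** Keep Hypothesis 1 and the data collection as they are, and add the following to the analysis and report:

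- The mean or median change in calcium and in estradiol, in assay units, with 95% confidence intervals. Judge each interval against a clinically justified limit stated by the investigators. Where no limit is stated, present the result as estimation only.
- Among all treated women with data, the number exceeding the protocol's existing calcium limits and the number judged to meet the Section VII.c estradiol criterion, each with an exact two-sided 95% interval.
- A listing of individual estradiol changes, by menopausal status if it was recorded. The eligibility criteria admit both pre- and post-menopausal women, but Table 1 and the demographics paragraph do not list it as a collected variable.
- A statement that p≥0.05 is inconclusive and is not evidence of safety.
- A post hoc label on any analysis or limit added after the data were seen. The SAP is written in the past tense, so this may apply to all of them.

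A limit does not guarantee a firm conclusion. With n=20 and a true change of zero, the 95% interval has an 80% chance of lying wholly inside a symmetric limit only if that limit is about 0.76 SD. If only a rise matters, the figure is 0.66 SD.

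The cost is a few extra tables, largely from data already planned for collection. The estradiol count will rest on clinical judgement, and the safety statement becomes less favourable: with no events, for example, only rates above 16.8% (n=20) or 13.7% (n=25) are excluded.
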